1.1 BACKGROUND ON MULTIPLE SCLEROSIS

1.1.1 Multiple Sclerosis

MS is a chronic, inflammatory, and demyelinating disease of the human CNS, which affects approximately 2.3 million people worldwide, with the highest prevalence in North America and Europe, at 140 and 108 per 100,000, respectively (Multiple Sclerosis International Federation 2013). Typically, young adults are affected; 70%–80% of patients have an age of onset (i.e., initial clinical presentation to a physician) of between 20 and 40 years (Anderson et al. 1992; Noonan et al. 2002). MS is a heterogeneous disorder both pathophysiologically and phenotypically. This variability can be seen, on the basis of clinical course, via magnetic resonance imaging (MRI) scan assessments, and pathological analysis of biopsy and autopsy material (Luccinetti et al. 2000).

The disease manifests itself as a variety of neurological deficits attributable to dysfunction of CNS components, such as the spinal cord, brainstem, optic nerve, cerebellum, and cerebrum. Deficits can include weakness, loss of coordination, visual loss, cognitive impairment, and loss of bowel and/or bladder control, among others. These system-based symptoms are generally superimposed on more chronic, pervasive symptoms, including mood disorder, neuropathic pain, fatigue, and sexual dysfunction.

1.1.2 Ocrelizumab

OCR binds to human CD20 with high affinity, selectively depleting B cells through several mechanisms, including antibody-dependent cell-mediated phagocytosis, antibody-dependent cellular cytotoxicity, complement-dependent cytotoxicity, and induction of apoptosis.

OCR is also known as Ro 4964913, PRO70769, and rhuMAb 2H7 (refer to the Ocrelizumab Investigator's Brochure for further information).

1.1.3 Sponsor Experience with Anti-CD20 Compounds in Multiple Sclerosis

The ongoing clinical development program to investigate the safety and efficacy of OCR in patients with both relapsing forms (i.e., RMS and relapsing-remitting MS [RRMS]) and primary progressive MS (PPMS) includes an ongoing open-label extension (OLE) of the Phase II Study WA21493/ACT4422G for RRMS patients and three ongoing Phase III pivotal trials: 2 in RMS (WA21092 and WA21093) and 1 in PPMS (WA25046).

1.1.3.1 Ocrelizumab in Relapsing Forms of Multiple Sclerosis (RMS)

Study WA21493 (which started in January 2008) is a Phase II, randomized, multicenter, placebo-controlled, double-blind, dose-finding study to evaluate the efficacy and safety of OCR in patients with RRMS. The controlled treatment period of Study WA21493 was completed at Week 24, and the open-label period of the study is ongoing. Data from the 96-week treatment period and the 48-week treatment-free period (Week 144 data) are presented in the Ocrelizumab Investigator's Brochure.

Data presented below are from the completed double-blind, double-dummy treatment period of the two pivotal Phase III studies in RMS (Studies WA21092 and WA21093) up to the clinical cutoff dates of 2 April 2015 and 12 May 2015, respectively. The efficacy results as well as the pooled analysis from these pivotal studies show that OCR suppresses relapses and disease progression (clinical and subclinical disease activity) compared with interferon (IFN) β -1a 44 μ g SC in patients with RMS over the course of 2 years (96 weeks).

Efficacy outcomes were consistent between trials and across the primary and key clinical and imaging secondary endpoints.

In comparison with IFN β -1a 44 μ g SC, OCR 600 mg demonstrated:

- Relative reductions of 46% and 47% for the primary endpoint of protocol-defined annualized relapse rate in Studies WA21092 and in WA21093, respectively (both $p < 0.0001$)
- A 40% risk reduction for 12-week confirmed disability progression (CDP) in the pooled Study WA21092/WA21093 analysis ($p = 0.0006$). Each individual trial also demonstrated a significant reduction of 12-week CDP (43% reduction [$p = 0.0139$] in Study WA21092 and 37% [$p = 0.0169$] in Study WA21093).
- Relative reductions of 94% and 95% in the number of T1 gadolinium (Gd)-enhancing lesions in Studies WA21092 and WA21093, respectively (both $p < 0.0001$)
- Relative reductions of 77% and 83% in the total number of new and/or enlarging T2 lesions in Studies WA21092 and WA21093, respectively (both $p < 0.0001$)
- A 33% relative increase in proportion of patients with 12-week confirmed disability improvement (CDI) in the pooled Study WA21092/WA21093 analysis ($p = 0.0194$). Study WA21092 demonstrated a 61% relative increase in the proportion of patients with 12-week CDI ($p = 0.0106$), whereas in Study WA21093, there was no statistically significant difference between treatment groups (14% relative increase, $p = 0.4019$).
- A 40% risk reduction for 24-week CDP in the pooled Study WA21092/WA21093 analysis ($p = 0.0025$). Each individual trial also demonstrated a significant reduction of 24-week CDP (43% reduction [$p = 0.0278$] in Study WA21092 and 37% [$p = 0.0370$] in Study WA21093).

- Relative reductions of 57% and 64% (both $p < 0.0001$) in the total number of new T1 hypointense lesions (chronic black holes) in Studies WA21092 and WA21093, respectively

OCR also showed numerically superior outcomes in additional secondary efficacy endpoints in the following hierarchical order (for results where the formal testing procedure had previously concluded, p-values are indicated as "non-confirmatory"):

- Greater mean improvement in the Multiple Sclerosis Functional Composite Scale from baseline to Week 96 in Study WA21092 ($p = 0.3261$) and Study WA21093 ($p = 0.0040$)
- Relative reduction in rate of brain volume loss from Week 24 to Week 96 of 22.8% in Study WA21092 (non-confirmatory, $p = 0.0042$) and 14.9% in Study WA21093 ($p = 0.0900$)
- Higher mean change in SF-36 Physical Component Summary score from baseline to Week 96 in Study WA21092 (non-confirmatory, $p = 0.2193$) and Study WA21093 (non-confirmatory, $p = 0.0404$)
- 74% and 81% relative increases in the proportion of patients with no evidence of disease activity in Studies WA21092 and WA21093, respectively (non-confirmatory, $p < 0.0001$ for both studies in patients with Expanded Disability Status Scale [EDSS] ≥ 2)

Robust data from the two pivotal Phase III studies WA21092 and WA21093 presented above provide compelling evidence of the efficacy of OCR in patients with RMS.

1.1.3.2 Safety in Multiple Sclerosis

Safety data presented below are from the completed controlled treatment periods of the two pivotal Phase III studies in RMS (WA21092 and WA21093) and the Phase III study in PPMS (WA25046). For more information on data from controlled treatment periods and OLE periods from ongoing studies, refer to the Ocrelizumab Investigator's Brochure. In the 96-week controlled treatment period of the Phase III RMS studies (WA21092 and WA21093), a total of 1651 patients received study drug and were included in the safety analyses of the pooled data (IFN β -1a: 826 patients; OCR: 825 patients).

The safety profile in the IFN β -1a treatment group was consistent with the labeled safety information available for IFN β -1a. Compared with results from the Phase II study in RRMS (WA21493), there were no new or unexpected safety findings associated with OCR during the 96-week controlled treatment period.

The number of patients who experienced any adverse event (83.3% in both groups) and the total number of adverse events (IFN β -1a: 4141 adverse events; OCR: 4194 adverse events) were well balanced between the two treatment groups; the majority of adverse events were Grade 1 or Grade 2. The proportion of patients who experienced a serious adverse event (IFN β -1a: 8.7% vs. OCR: 6.9%) was similar between treatment

groups. Overall, the rates of adverse events, including serious, remained stable with additional exposure to OCR.

A total of 725 patients in the Phase III PPMS controlled treatment period received study drug and were included in the safety analysis (placebo: 239 patients; OCR: 486 patients). The proportion of patients who experienced at least one adverse event was 90% in the placebo treatment group compared with 95.1% in the OCR treatment group; the majority of adverse events were Grade 1 or 2. The proportion of patients who experienced a serious adverse event (placebo: 22.2% vs. OCR: 20.4%) was similar in both groups. The intensity of most serious adverse events was reported as Grade 3.

Further details are provided in the periodically updated Ocrelizumab Investigator's Brochure.

To date, there are no known major safety concerns but known risks for patients being treated with OCR; these are discussed in Section 5.1. Also refer to the latest Ocrelizumab Investigator's Brochure.

1.1.4 Vaccine Response with Ocrelizumab

OCR significantly and rapidly reduces the number of peripheral CD20+B cells. In the Phase II study WA21493, all patients had completely depleted CD19+ cells by Day 15 (99% mean and median change from baseline) and by Week 24, no patient had demonstrated any return of peripheral CD19+ cell counts to baseline values or to the lower limit of normal (LLN) of 80 cells/ μ L, (i.e., the protocol-defined measure of recovery). B cells repleted for >50% of the patients in all treatment groups by Week 144, except for in the OCR 1000 mg group (where 56.4% of the patients were still depleted at Week 144). The relevance of patients not having repleted B-cell levels (i.e., returned to LLN or baseline) to their response to vaccination is not known.

Results from the Immunization Study Period of this study BN29739 indicate that patients being treated with OCR may have an attenuated humoral response when immunized with an inactivated vaccine. The detailed BN29739 study results can be found in the current version of the Ocrelizumab Investigator's Brochure.

An integrated analysis of MS patients treated with OCR treatment revealed that after treatment with OCR over 2 years, the proportion of patients with positive antibody titers against Streptococcus pneumoniae, mumps, rubella, and varicella was generally similar to the proportions at baseline.

1.2 STUDY RATIONALE AND BENEFIT-RISK ASSESSMENT

This study (BN29739) is being performed to characterize humoral immunity to a variety of antigens by evaluating immunization responses in patients with RMS who are treated with OCR.

This study plans to use the following vaccines to evaluate different immune response pathways after administration of a course of OCR in patients with RMS:

- The TT-containing vaccination was chosen to assess the T-cell dependent anamnestic humoral response.
- The 23-valent PPV (23-PPV) vaccination was chosen to assess a mostly T-cell independent or pure 'B-cell' humoral response.
- KLH was chosen to explore immune response to neo-antigen.
- The influenza vaccination was chosen as it is considered important from a clinical perspective.
- The booster 13-valent conjugate pneumococcal vaccine (13-PCV) was chosen to assess the clinical efficacy of the 23-PPV vaccine followed by the booster 13-PCV compared to 23-PPV vaccine alone.

Characterization of the humoral immune response in RMS patients who have received OCR will provide guidance regarding the efficacy and safety of vaccine administration in these patients. Please refer to Section 3.1 for further details on study design.

Substantial measures have been taken to enroll only appropriate patients and to decrease the risk to patients who participate in this study. Refer to eligibility criteria in Section 4.1 and the safety plan in Section 5.1, respectively.

2. OBJECTIVES

2.1 PRIMARY OBJECTIVE

The primary objective for this study is as follows:

- To characterize the humoral immune response (IgG) to TT vaccine in patients with RMS who are treated with OCR (Group A), compared with that of patients with RMS who are not treated with OCR (Group B).

2.2 SECONDARY OBJECTIVES

The secondary objectives of this study are:

1. To characterize the humoral immune response (IgG) to the 23-PPV in Group A (Groups A1 and A2) patients compared with Group B patients.
2. To characterize the humoral immune response (IgG) in OCR-treated patients to 23-PPV boosted by a subsequent 13-PCV booster (Group A1) compared with unboosted 23-PPV (Group A2).
3. To characterize the humoral immune response (IgG and IgM) to KLH in Group A patients compared with Group B patients.
4. To characterize the humoral immune response (HI titers) to influenza vaccine in OCR-treated patients (Group A2) patients compared with patients not treated with OCR (Group B).

5. To evaluate the long-term effects of OCR on MRI parameters of disease activity during the Optional Ocrelizumab Extension (OOE) Period of the study.

Group A will be split into Group A1 (patients will receive the booster 13-PCV), and Group A2 (patients will receive the influenza vaccine; see Section [3.1](#)).

2.3 SAFETY OBJECTIVES

The safety objectives for this study are to collect additional data on the safety of OCR.

3. STUDY DESIGN

3.1 DESCRIPTION OF STUDY

This Phase IIIb, multicenter, randomized, open-label study is designed to evaluate immune response to vaccines after administration of a dose of OCR (i.e., a dual infusion of OCR 300 mg on Day 1/Week 1 [Dose 1 Infusion 1] and Day 15/Week 2 [Dose 1 Infusion 2]) in patients with RMS.

Following screening, approximately 100 adult patients will be randomized into Groups A and B (2:1; active:control) to compare responses to immunization. Patients in Group B are to receive immunization with TT-containing adsorbed vaccine, 23-PPV, influenza vaccine, and repeated administration with KLH. Group B patients will not receive OCR but will remain on no MS-specific disease-modifying therapy (DMT) or continue with IFN- β treatment until optional OCR treatment at the end of the Immunization Study Period.

Patients in Group A are to first receive OCR (Day 1/Week 1 [Dose 1 Infusion 1] and Day 15/Week 2 [Dose 1 Infusion 2]), and 12 weeks post-OCR treatment, are to receive a similar immunization course to Group B. Group A will be further subdivided into two groups to evaluate the effectiveness of a booster 13-PCV vaccination or of influenza vaccination.

For the primary objective and for secondary objectives 1 and 3 (see Sections [2.1](#) and [2.2](#), respectively), Group A (active) will be compared with Group B (control).

To determine the outcomes of secondary objectives 2 and 4, patients in Group A will be split into two groups with 50% of patients in each group (Groups A1 and A2). Patients will be assigned to either Group A1 or A2:

- Group A1 will receive booster 13-PCV (approximately 33 patients)
- Group A2 will receive the influenza vaccine (approximately 33 patients but a minimum of 30 patients).

A minimum of 30 patients will be assigned to Group A2 during the first influenza season. If a minimum of 30 patients (a maximum of 33) are assigned to Group A2 and receive the first year's influenza vaccine, all remaining patients in Group A will be assigned to

Group A1 and receive the 13-PCV booster. If less than 30 patients have been assigned to Group A2 during the first influenza season, further patients assigned to Group A2 will have influenza vaccine visits during the subsequent influenza season (i.e., when the next year's vaccine becomes available).

The primary and secondary humoral immunity and immunophenotyping outcomes are to be measured by flow cytometry and quantitative Ig measurements.

Approximately 30–35 centers will participate in the study in the United States/North America. This study consists of up to five study periods:

- Screening Period
- Immunization Study Period

Group A: Immunization Study Period and OCR treatment starts at Day 1/Week 1. Patients will receive 300 mg of open-label OCR on Day/Week 1 (Dose 1 Infusion 1) and Day 15/Week 2 (Dose 1 Infusion 2). Patients in Group A will be split and be assigned to either Group A1 (booster 13-PCV) or Group A2 (influenza vaccine). At Day 85/Week 12 patients will start to receive immunizations and undergo post-immunization assessments. For all patients in Group A, the Immunization Study Period will end on Day 169/Week 24.

Group B: Patients will not receive OCR. At Day 1/Week 1, patients will start to receive immunizations and undergo post-immunization assessments. For Group B, the Immunization Study Period will end at Day 84/Week 12.

The timing of immunizations and post-baseline assessments are detailed in [Appendix 1](#).

[figure not shown]
- Optional OCR Extension (OOE) Period:
 - **Groups A1 and A2:** Patients who complete the 24-week immunization study period will have the option for retreatment with a single infusion of 600 mg OCR (Dose 2) at Day 169/Week 24 and subsequent single infusions (600 mg OCR) at intervals of 24 weeks provided that he or she meets the OOE retreatment criteria and chooses to receive retreatment.
 - **Group B:** Patients who complete the 12-week immunization study period will have the option to receive OCR in the OOE; the first dose will be administered as two single infusions of 300 mg, on Day 84/Week 12 (Dose 1 Infusion 1) and Day 98/Week 14 (Dose 1 Infusion 2), and subsequent doses will be administered as single 600 mg infusions (Dose 2, Dose 3, etc.) at intervals of 24 weeks provided that he or she meets the OOE retreatment criteria and chooses to receive retreatment. Group B patients who do not qualify for and/or do not choose treatment with OCR at Week 12 will complete the study at Week 12 and will **not** enter safety follow-up.

Please note that the OOE will continue with all patients who are able to receive OCR as per local guidelines, or unless the Sponsor decides to terminate the OCR program for MS; however, the OOE will not exceed 4 years after the last patient last visit in the Immunization Study Period. *At the end of the OOE, patients may choose to continue on commercially available OCR.*

- Safety Follow-Up (SFU) Period: *Patients who discontinue treatment early for any reason and patients who complete the study treatment period will be followed up for 48 weeks after the last infusion of OCR. When patients begin an alternative treatment for MS (see Section 4.6.3.1 on prohibited therapies), or start treatment with commercial OCR, they will be discontinued from the SFU and from the study.*

A schedule of assessments is provided in [Appendix 1](#). Study Schemas are provided in [Figure 1](#) and [Figure 2](#).

Figure 1 Schema of Study Periods

OCR=ocrelizumab; OOE=Optional Ocrelizumab Extension Period; SFU=safety follow-up.

Figure 2 Study Schema

[figure not shown]

Figure 2 Study Schema (cont.)

KLH=keyhole limpet heamocyanin; *OCR*=*ocrelizumab*; PCV=pneumococcal conjugate vaccine; PPV=polysaccharide pneumococcal vaccine; TT=tetanus toxoid-containing vaccine; Wk=week

Influenza vaccine: Group B: The influenza vaccine can be given any time between Week 1 and 12. If a patient needs to receive the vaccine after Week 12, the *OCR* infusion can be delayed. For patients in Group A2 and Group B who, as per the Schedule of Assessment, are due to receive the influenza vaccine during their country-specific influenza vaccine blackout period, administration of the vaccine should be given prior to the start of this blackout period.

***Group A split:** Patients assigned to Group A2 will receive the influenza vaccine. Patients assigned to Group A1 will receive the 13-PCV booster.

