- Significant, uncontrolled disease, such as cardiovascular (including cardiac arrhythmia), pulmonary (including obstructive pulmonary disease), renal, hepatic, endocrine, or gastrointestinal or any other significant disease that may preclude a patient from participating in the study
- Congestive heart failure (New York Heart Association III or IV functional severity)
- Known active bacterial, viral, fungal, mycobacterial infection or other infection (including tuberculosis [TB] or atypical mycobacterial disease [but excluding fungal infection of nail beds]) or any major episode of infection requiring hospitalization or treatment with IV antibiotics within 4 weeks prior to baseline visit or oral antibiotics within 2 weeks prior to baseline visit
- History or known presence of recurrent or chronic infection (e.g., HIV, syphilis, TB)
- History of recurrent aspiration pneumonia that required antibiotic therapy
- History of cancer, including solid tumors and hematological malignancies (except basal cell, *in situ* squamous cell carcinomas of the skin, and *in situ* carcinoma of the cervix of the uterus that have been excised and resolved, with documented clean margins on pathology)
- Any concomitant disease that may require chronic treatment with systemic corticosteroids or immunosuppressants during the course of the study
- History of alcohol or drug abuse within 24 weeks prior to randomization
- History of or currently active primary or secondary immunodeficiency
- Treatment with any investigational agent within 24 weeks of screening (Visit 1) or 5 half-lives of the investigational drug, whichever is longer, or treatment with any experimental procedure for MS (e.g., treatment for chronic cerebrospinal venous insufficiency)
- Receipt of any pneumococcal vaccine within 5 years prior to screening
- Previous exposure to KLH
- Previous immunization with any tetanus-containing vaccine within 2 years prior to screening
- If scheduled as per protocol to receive the 2015/2016 vaccine and has already received the 2015/2016 vaccine or if scheduled as per protocol to receive the 2016/2017 vaccine and has already received the 2016/2017 vaccine.

- Receipt of a live vaccine within 6 weeks prior to randomization*

**Vaccinations before baseline: in rare cases where a live vaccine must be administered by the patient's physician, the screening period may need to be prolonged but cannot exceed 8 weeks.*

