4.4.2.5 Seasonal Influenza Vaccine

The influenza vaccine is indicated for immunization against influenza caused by the influenza strains included in the vaccine. The inactivated (or recombinant) vaccine has

been chosen for this study to assess antibody production for a commonly used clinically relevant antigen.

Group A2 patients can receive the influenza vaccine at any time between Day 85/Week 12 and Day 140/Week 20.

Group B patients will receive the influenza vaccine as an IM injection in the deltoid muscle at any time between Day 1/Week 1 and Day 84/Week 12. If a patient needs to receive the influenza vaccine after Week 12, the optional OCR infusion must be delayed.

Group A1 patients can receive the influenza vaccine at any time at the discretion of the investigator.

Refer to the label for dosing and administration guidance.

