4.4.2.4 Influenza Vaccine Response

Between-group comparisons of influenza vaccine response require comparison of Groups A2 and B. As noted above in Section 4.4.2.2, comparisons between Groups A2 and B should be interpreted with some caution, since patients were not assigned to Group A2 randomly (patients were randomized to Group A or B, and within Group A were non-randomly assigned to Group A1 or A2, based on seasonality considerations).

The number and percentage of patients in Groups A2 and B who achieve seroprotection, defined as specific HI titers >40 at 4 weeks after vaccination, will be presented by treatment group. The difference between Groups A2 and B in seroprotection rates, and the associated 95% CI will also be presented using a normal approximation method.

The number and percentage of patients in Groups A2 and B who achieve a 2-fold increase in specific HI titers at 4 weeks after vaccination will be presented by treatment group. The difference between Groups A2 and B in the proportion of patients achieving a 2-fold increase, and the associated 95% CI will also be presented using a normal approximation method.

The number and percentage of patients in Groups A2 and B who achieve a 4-fold increase in specific HI titers at 4 weeks after vaccination will be presented by treatment group. The difference between Groups A2 and B in the proportion of patients achieving a 4-fold increase, and the associated 95% CI will also be presented using a normal approximation method.

The number and percentage of patients in Groups A2 and B who achieve seroconversion at 4 weeks after vaccination, defined as a pre-vaccination antibody titer <10 and a HI titer >40 at 4 weeks after vaccination, will be presented by treatment group. The difference between Groups A2 and B in seroconversion rates, and the associated 95% CI will also be presented using a normal approximation method.

Strain-specific GMTs in patients in Groups A2 and B measured 4 weeks after vaccination will be summarized descriptively by treatment group using the same summary statistics as presented in Section 4.4.1 for the primary immunology endpoint.

Strain-specific GMT ratio (post-vaccination:pre-vaccination) in patients in Groups A2 and B will be summarized descriptively by treatment group; summary statistics calculated will include mean, median, SD, minimum, and maximum.

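### The SAP plans no season-matched or season-stratified comparison of Group A2 with Group B for influenza response, so the difference may be partly confounded by vaccine season

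*Protocol*

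**What the plan says.** Protocol 3.1 directs Group A2 towards the first season: "A minimum of 30 patients will be assigned to Group A2 during the first influenza season". The next sentence closes the group once it is filled. It begins "If a minimum of 30 patients (a maximum of 33) are assigned to Group A2 and receive the first year's influenza vaccine" and sends every remaining Group A patient to A1. The second season is a fallback for a shortfall below 30, in which case "further patients assigned to Group A2 will have influenza vaccine visits during the subsequent influenza season".

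All of Group B is to receive influenza vaccine, and no season quota is set for it. Protocol 4.4.2.5 defines the windows from each patient's own Day 1. For A2: "Group A2 patients can receive the influenza vaccine at any time between Day 85/Week 12 and Day 140/Week 20". For B: "at any time between Day 1/Week 1 and Day 84/Week 12", or later if the optional ocrelizumab infusion is delayed.

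Two vaccine years are foreseen in Protocol 4.1.2: "If scheduled as per protocol to receive the 2015/2016 vaccine and has already received the 2015/2016 vaccine" and "if scheduled as per protocol to receive the 2016/2017 vaccine and has already received the 2016/2017 vaccine". Neither is tied to a named group.

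SAP 4.4.2.4 states: "Between-group comparisons of influenza vaccine response require comparison of Groups A2 and B". For each response proportion it gives the A2 minus B difference with a normal-approximation 95% CI, in patients who complete the Immunization Study Period (SAP 4.1.2 and 4.4). It notes that A2 was filled non-randomly for seasonal reasons and asks for some caution. It has no season term, restriction or stratification.

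**The concern.** Antibody response to influenza vaccine can differ between seasons, through vaccine composition and through the titers that patients already carry. If A2 sits mostly in the first season and B is spread over two, part of any A2 minus B difference reflects the vaccine year rather than ocrelizumab. A reader of the planned tables could not tell how much, because nothing shows the season mix of either group.

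The rest of the SAP does not fill the gap. Section 4.3.7 summarizes pre-vaccination strain-specific titers by group, not by season. Section 4.4.5 offers optional sensitivity analyses that exclude patients with major deviations or other data issues. Section 4.4.6 plans no subgroup analysis. No stratification factor is stated for the randomization (Protocol 4.2, SAP 3.1).

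The result is used: Protocol 5.1.1.6 draws on this study when it discusses influenza vaccination under ocrelizumab. The size of the difference therefore matters, even though the endpoint is secondary and descriptive.

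**Working it through.** **The plan's own figure.** The documents give no precision figure for A2 versus B. The only one, 0.201, is for the tetanus primary endpoint at 70% response in both groups (Protocol 6.1, SAP 2.3). With half-width = 1.96 × √[0.21 × (1/n₁ + 1/n₂)], a 67:33 split gives 0.191 and 60:30 gives 0.201, so the figure fits about 90 evaluable patients. It does not bear on this point. I borrow only the formula and the 70%, which is an assumption when applied to influenza.

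**Bias.** Let fA and fB be the shares of A2 and B vaccinated in season 1, r₁ and r₂ the control response rates in the two seasons, and δ the ocrelizumab effect, taken as equal in both seasons.

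- Expected A2 rate: r₂ + δ + fA(r₁ − r₂)
- Expected B rate: r₂ + fB(r₁ − r₂)
- Crude difference: δ + (fA − fB)(r₁ − r₂)

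The bias is therefore (fA − fB)(r₁ − r₂). Its sign depends on which season gives the higher response. The documents supply none of fA, fB, r₁ or r₂, so every row below is illustrative.

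| fA | fB | Season difference 10 / 20 / 30 points: bias in points |
|---|---|---|
| equal to fB | any | 0 / 0 / 0 |
| 0.80 | 0.75 | 0.5 / 1 / 1.5 |
| 0.90 | 0.50 | 4 / 8 / 12 |
| 1.00 | 0.50 | 5 / 10 / 15 |

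**Precision after the change.** At 70% response, the pooled half-width with 33 v 33 is 1.96 × √[0.21 × (1/33 + 1/33)] = 0.221.

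With Mantel-Haenszel weights w = ab/(a + b) in each season (a patients in A2, b in B), the stratified half-width is 1.96 × √[0.21/(w₁ + w₂)]. With A2 split 30/3:

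- B 25/8: w = 13.64 + 2.18, half-width 0.226
- B 17/16: w = 10.85 + 2.53, half-width 0.246
- B 8/25: w = 6.32 + 2.68, half-width 0.299

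If all 33 A2 patients are in season 1 and B is restricted to season 1, the half-width is 0.238 with 25 B patients, 0.274 with 16 and 0.354 with 8. The loss of precision is large only when the season mixes differ greatly, which is also when the pooled estimate is most exposed.

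**The case against.** The strongest reply is that the SAP already discloses the problem. It gives seasonality as the reason for the A1/A2 split and advises caution on A2 versus B. The pre-vaccination titers will be tabulated, fold-rise and titer-ratio endpoints use each patient's own baseline, and there is no hypothesis test. All of this is true and limits the consequence. However, the caution concerns how A2 was filled. It does not say that B may have received a different vaccine, and it offers no means of sizing the effect. A patient's own baseline does not remove a season difference in response to the vaccine.

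A second reply is that the endpoints are strain-specific. That separates seasons only for a strain found in one year's vaccine, and only if the denominator is limited to its recipients, which the SAP does not state. Strains common to both vaccines remain pooled.

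Three stronger readings are tempting, and the documents do not support them.

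- A reader might infer that season and ocrelizumab are in fact confounded. B's season split is never given, and the fallback sentence would spread A2 over both seasons, which may reduce the imbalance.
- A reader might take 30 to 33 A2 patients under 2:1 randomization to mean only 15 to 17 concurrent B patients, putting about half of B in another season. That requires every first-season Group A patient to go to A2. Protocol 3.1 also describes an even split of Group A, and Protocol 3.3.2.5 places the split at randomization. If A1 and A2 fill in parallel, up to about 33 B patients could be concurrent.
- A reader might regard a within-season contrast as the randomized comparison. It is not: A2 is selected non-randomly within Group A, and the windows (Weeks 12 to 20 against Weeks 1 to 12) can put patients randomized together into different vaccine seasons.

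**Conclusion.** The point holds as a gap in the planned analysis, not as a demonstrated bias. A2 is preferentially filled in the first season, B has no matching rule, two vaccine years are foreseen, and the A2 minus B difference is crude. Partial confounding by vaccine season is therefore possible, with unknown size and sign. It is zero if the season mixes match. It reaches 5 to 15 points only under the joint assumptions that all of A2 and half of B are in season 1 and that response differs by 10 to 30 points between seasons.

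Only secondary objective 4 is affected. The tetanus primary endpoint compares all of Group A with Group B and is untouched. This is a cheap improvement to a descriptive comparison.

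**What to change.** In SAP 4.4.2.4:

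1. Tabulate vaccine season by group for A2 and B. If the mixes agree, this table alone closes the question.
2. Where the vaccine season or product identifies the strains, limit each strain's analysis to patients given a vaccine containing that strain.
3. Beside the pooled A2 minus B difference, report a season-stratified one: Mantel-Haenszel, or the within-season estimate if A2 lies entirely in one season. State that it is still not a fully randomized comparison.

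Protocol 5.1.1.6 shows that results from the Immunization Study Period are already known, so the analysis should be labelled supplementary.

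The cost is SAP wording, some extra tabulation and a wider interval. At an assumed 70% response, the half-width is about 0.25 to 0.30 for the less balanced splits shown, against 0.22 pooled. Steps 1 and 3 need only the vaccination date. Step 2 may need the product: Protocol 4.4.2.5 allows inactivated or recombinant vaccine, and the documents do not say that composition is recorded.
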